Hypothesis 2: Increased uptake of ^{11}C -ER176 associates with a shift towards pro-inflammatory macrophage milieu on tissue assessment made by targeted biopsies of gastric muscle

B. Background and Significance

[figure not shown]

Fig 1: Molecular structure of ^{11}C -ER176.

Gastroparesis as a complication of diabetes mellitus: Gastroparesis is a chronic disorder of the upper GI tract characterized by delayed gastric emptying of solids and/or liquids in the absence of mechanical obstruction of the gastric outlet¹. Cardinal symptoms include nausea, vomiting, bloating, postprandial fullness, early satiety and abdominal pain. In one study, DG accounted for almost a third of the overall gastroparesis cases²⁴. In the diabetes control and complications trial, delayed gastric emptying was associated with greater HgbA1c, longer duration of diabetes, lower R-R variability on electrocardiogram, nephropathy, retinopathy, and greater GI symptoms²⁵. In a study from the type 1 diabetes exchange clinic registry, females are more likely to have gastroparesis than males²⁶. Another population-based study showed a 4-fold higher prevalence of gastroparesis in women when compared with men²⁷. Patients with DG have a significant impairment of their quality of life; especially symptoms of nausea, bloating and chronic pain^{28, 29}. In spite of the frequent occurrence of this highly morbid complication of diabetes mellitus, there is a significant dearth of treatment options.

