Innovation: This proposal is innovative from both biological and technical standpoints. Strong animal and human data generated by our group and others demonstrate macrophage activation in gastroparesis. This has been mechanistically shown to play a role in gastric motor dysfunction via injury to ICC. There is currently no noninvasive way to determine immune dysregulation in the gastric muscle. More broadly, macrophage dysfunction also plays a role in other inflammatory disorders of the gut such as inflammatory bowel disease. Technological advancements in ligands for PET imaging have already led to emergence of its role in studying neuroinflammation as well as joint inflammation. We plan to use the latest generation TSPO radioligand, ¹¹C-ER176, for delineating macrophage activation in DG. We will validate imaging findings with state-of-art sampling of gastric muscle followed by isolation of immune cells and using single cell-based techniques to determine transcriptional changes in immune cells. If successful, these studies will provide pilot data for larger studies aimed at determining immune dysregulation in diabetic gastroenteropathy as well as other inflammatory GI disorders.

C. Preliminary Studies

Macrophage cell population in gastric muscle expresses TSPO: In preliminary studies, human gastric muscle tissues (idiopathic gastroparesis) were dissociated followed by magnetic separation and isolation of CD45⁺ immune cells. Libraries were prepared using 10x Genomics Library Kits and sequenced on HiSeq4000. The t-distributed stochastic neighbor embedding (t-SNE) plot revealed 12 clusters of CD45⁺ cells (**Figure 3a**). CD68, a type I transmembrane glycoprotein, heavily expressed in cells of monocyte/macrophage lineage forming a discrete cluster (**Figure 3b**). TSPO showed predominant expression in the CD68⁺ subset of cells (**Figure 3c**). This suggests that gastric muscle contains immune cells that are TSPO⁺, hence, providing proof-of-concept data that ¹¹C-ER176 PET imaging targeting TSPO should demonstrate uptake *in vivo* in humans. TSPO has been strongly associated with an activated or pro-inflammatory macrophage subtype. In a recent study, during M2 (anti-inflammatory) polarization, TSPO expression was decreased¹⁴. A TSPO antagonist enhanced anti-inflammatory polarization. Additional studies have also demonstrated TSPO being an imaging target for identifying pro-inflammatory macrophage milieu^{12, 19}.

[figure not shown]

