Upper endoscopy with endoscopic ultrasound and targeted biopsies of gastric muscle: A pregnancy test will be administered to women of child-bearing potential. Upper endoscopy will be performed only on DG patients only. The endoscopy will be performed within 12 weeks of the participant's PET/CT scan, this will allow more scheduling flexibility for the participant and study team. During the endoscopy procedure an additional procedure known as endotracheal intubation may be performed to keep the airway open and assist with breathing. This will vary from case to case and is determined by the anesthesiologist assisting with or the physician performing the endoscopy. The echoendoscope (Aloka Arietta 850; Olympus, Center Valley, PA) will be advanced into the gastric lumen and a site targeted for EUS-guided core biopsies based on findings of the PET scan. Fine needle biopsy of the gastric wall will be performed using a 19 G needle (SharkCore; Medtronic, Minneapolis, MN) passed through the echoendoscope and across the entire gastric wall ensuring a full thickness (mucosa to serosa) core tissue sample. Sampling of the uninvolvled region will be done to serve as control. In patients who do not have clear signal on PET/CT, sampling will be done from gastric antrum and body to act as negative control. All endoscopic procedures will be done by advanced endoscopist [REDACTED] [REDACTED]. EUS-guided core biopsy is a safe procedure associated with a low risk of adverse events.

Assessment of gastric macrophages: After tissue dissociation, using technique similar to that shown in the preliminary data, cells will be sorted and profiled using the Fluidigm (San Francisco, CA) Helios cytometry by time of flight (CyTOF) mass spectrometry system. After cleanup in FloJo to obtain singlets, data will be analyzed using the R-based CytofKit tool^{38, 39}. In an approach that was not biased towards a limited subset of cell types, cellular subtypes will be identified and counted after labeling with a panel of 32 antibodies to distinguish monocytes and tissue myeloid cells from the other immune cells (CCR2, CD24, CD64, Ly6C, CD115/CSF1R, CD38, CD8a, Ly6G, CD11b (Mac-1), CD3e, CX3CR1, MERTK, CD11c, CD4, ESAM, PDL-1, CD14, CD44, F4/80, PDL-2, CD161 (NK1.1), CD45, FcER1, SiglecH, CD19, CD45R (B220), I-A/I-E, SIRPa (CD172a), CD206 (Mrc1), CD62L, IL2RA, CD25, TER-119). Data will be displayed as tSNE maps and heatmaps.

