Endpoints and statistical analysis: The biodistribution of ¹¹C-ER 176 in the stomach using time activity curves and other described imaging metrics will be the primary endpoint. Correlative analysis will be done between biodistribution on ¹¹C-ER176 and pro-inflammatory markers on cellular expression using CyTOF. The proposed study will provide means and standard deviations for larger investigation in this area. Considering the robust expression of TSPO in gastric macrophages in our preliminary data, we expect to see uptake of TSPO ligand ¹¹C-ER 176 in the gastric muscle.

Anticipated results, potential pitfalls and alternative strategies: We anticipate finding that patients with DG will have significantly higher PET uptake of ¹¹C-ER176 compared to healthy volunteers. Additionally, we anticipate that the uptake will strongly associate with upregulation of TSPO and other pro-inflammatory markers like Ly6C and downregulation of anti-inflammatory markers like CCR2, CX3CR1 and CD206. Most second-generation TSPO radioligands have varying degrees of sensitivity to the single nucleotide polymorphism rs6971 in the TSPO gene⁴⁰, and this genotype sensitivity may vary depending upon the organ where it is expressed²². Therefore, some subjects who are low-affinity binders are excluded from analyses and the remaining subjects are corrected for being either high- or mixed-affinity binders. On the other hand, ¹¹C-ER176, a third-generation ligand, has shown little *in vitro* sensitivity to rs6971. However, *in vivo*, ¹¹C-ER176 was found to be sensitive to rs6971. Nevertheless, it allowed quantitation even in low affinity binders and had high non-displaceable binding potential, which suggests that its relative *in vivo* sensitivity to rs6971 may not impact clinical imaging²². Due to the small sample size of this feasibility study, we will be unable to select subjects with varying TSPO affinity genotype. However, if we see insufficient binding, we will determine the genotype.

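### The CyTOF panel for human gastric biopsies lists 6 to 8 mouse-designated targets out of 32, and neither pro-inflammatory marker named in the protocol can be measured with it as written

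*Combined protocol and SAP*

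**What the plan says.** Hypothesis 2 (section A, Specific Aims) is that higher tracer uptake "associates with a shift towards pro-inflammatory macrophage milieu on tissue assessment made by targeted biopsies of gastric muscle". The tissue is human: under section D, the endoscopy paragraph restricts endoscopic core biopsy to the patients with diabetic gastroparesis, of whom four are planned.

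Section D, Assessment of gastric macrophages, describes "labeling with a panel of 32 antibodies to distinguish monocytes and tissue myeloid cells from the other immune cells" and then lists the targets. Three stretches of the list matter here: "Ly6C, CD115/CSF1R, CD38, CD8a, Ly6G, CD11b (Mac-1), CD3e", "F4/80, PDL-2, CD161 (NK1.1), CD45, FcER1, SiglecH, CD19, CD45R (B220), I-A/I-E" and "CD206 (Mrc1), CD62L, IL2RA, CD25, TER-119". No species or clone is given for any antibody.

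The Endpoints and statistical analysis paragraph plans a correlation between tracer biodistribution and pro-inflammatory markers measured by CyTOF. It specifies no test, score or threshold. The Anticipated results paragraph gives the predicted directions. TSPO should rise with uptake, together with "other pro-inflammatory markers like Ly6C and downregulation of anti-inflammatory markers like CCR2, CX3CR1 and CD206".

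Section C (Preliminary Studies), working on human gastric muscle, identifies the macrophage cluster by "CD68, a type I transmembrane glycoprotein, heavily expressed in cells of monocyte/macrophage lineage", and reports TSPO mainly in that CD68-positive subset.

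**The concern.** The panel is to be run on human cells, yet several of its entries are names of mouse antigens or mouse alleles. I-A/I-E, for example, denotes mouse MHC class II. An antibody to such a target gives no usable signal on human tissue, or does not mark the intended population.

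This would be minor if it touched only lineage-exclusion channels. It also touches the one listed marker that the protocol names as pro-inflammatory. The other marker so named, TSPO, is the target of the tracer itself and is missing from the panel. CD68, which would tie a TSPO signal to macrophages as in the preliminary data, is missing too.

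At stake is the tissue validation of the imaging, one of the study's two hypotheses. The material is scarce: four patients, with one endoscopy described for each, sampled by full-thickness 19 G needle. Section F acknowledges bleeding and perforation risk and expects no direct benefit to the gastroparesis patients. The protocol describes no second endoscopy from which to replace a sample stained with the wrong reagents.

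**Working it through.** **Inputs.** The panel list comes from section D, Assessment of gastric macrophages. The named markers and their directions come from section D, Anticipated results. The preliminary macrophage marker comes from section C. The classification of a name as a mouse designation rests on standard antigen nomenclature, because the protocol states no species.

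**1. Reproduce the stated panel size.** Counting in list order:
- CCR2 to CD64: 3
- Ly6C to CD3e: 7
- CX3CR1 to CD44: 8
- F4/80 to I-A/I-E: 9
- SIRPa: 1
- CD206 to TER-119: 5

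3 + 7 + 8 + 9 + 1 + 5 = 33 names. IL2RA and CD25 are the same protein, so there are 33 − 1 = 32 distinct targets. The protocol's figure of 32 is reproduced, and the duplicate name is a tidying matter only.

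**2. Count the mouse designations.**
- Listed outright under a mouse name: Ly6C, Ly6G, F4/80, SiglecH, I-A/I-E, TER-119. That is 6.
- Listed under a CD number with a mouse label in brackets: CD161 (NK1.1) and CD45R (B220). That is 2 more. These are the weaker cases; CD161, for instance, has a human counterpart.

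Share of the panel: 6/32 = 18.8% without the bracketed labels, 8/32 = 25.0% with them. Targets not affected: 32 − 6 = 26, or 32 − 8 = 24.

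**3. Check the markers that carry the prediction.**

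| Marker | Role in the protocol | On the list? | Measurable in patients as listed? |
|---|---|---|---|
| TSPO | pro-inflammatory, expected up | no | no |
| Ly6C | pro-inflammatory, expected up | yes, mouse designation | no |
| CCR2 | anti-inflammatory, expected down | yes | yes |
| CX3CR1 | anti-inflammatory, expected down | yes | yes |
| CD206 | anti-inflammatory, expected down | yes | yes |
| CD68 | macrophage identity (section C) | no | no |

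Named pro-inflammatory markers measurable: 0 of 2. Named anti-inflammatory markers measurable: 3 of 3. General myeloid markers such as CD14, CD64, CD11b, CD11c and MERTK are listed and unaffected.

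**4. Set this against the planned analysis.** The correlation in the Endpoints paragraph is with pro-inflammatory markers. With the panel as listed, neither marker the protocol names for that purpose yields a value. What remains is the arm that the protocol itself labels anti-inflammatory, plus markers to which it assigns no direction.

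**The case against.** The strongest reply is that the list is shorthand. No clones are stated, the team has worked on human gastric muscle, and the laboratory may intend human reagents whatever names were carried into the text. That is possible, and it is why the remedy is a reconciliation of the text. It does not dispose of the point. Ly6C reappears in the Anticipated results paragraph as a predicted finding, so the mouse designation has entered the hypothesis as well as the reagent list. TSPO and CD68 are absent whatever clones are used.

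A second reply is that Hypothesis 2 concerns a macrophage milieu, not one antigen. Ly6C is offered only as an example, and the background section reports CD206 already measured in the antrum of patients with diabetic gastroparesis. This stands. A reader might infer from the mouse names that Hypothesis 2 cannot be tested in patients at all, but the panel still carries all three named anti-inflammatory markers and several myeloid markers.

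A third reply is that the cytometry analysis is untargeted, and that the Innovation paragraph also mentions single-cell transcriptional methods, which might show TSPO or CD68 by another route. This stands in part. Unsupervised clustering cannot recover signal from a channel with no reactive antibody, however, and the Endpoints paragraph ties the correlation to CyTOF.

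A reader might also expect an empty Ly6C channel to be reported as absence of a pro-inflammatory shift. The protocol contains no rule that would read it that way, so this is a risk of misinterpretation and not a planned error.

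**Conclusion.** The point holds, with limits. Between 6 and 8 of 32 distinct targets (19% to 25%) are mouse designations in a panel meant for human tissue. They include the only listed marker named as pro-inflammatory, and the other named marker is not listed. As written, the planned correlation with named pro-inflammatory markers has no working channel (0 of 2), and the tissue evidence for Hypothesis 2 falls on the anti-inflammatory arm and general myeloid markers.

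Three stronger readings are not supported:
- **That the panel is mostly a mouse panel.** At least 24 of 32 targets are not mouse-designated.
- **That the absence of iNOS is a further gap.** The background section reports iNOS only in diabetic mice and does not rely on it in human tissue.
- **That CCR2 is given the wrong direction.** Nothing in the protocol allows that to be judged.

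The primary endpoint, PET biodistribution in the stomach, is untouched. The cytometry is a correlative analysis in four patients of a feasibility study. The conclusion assumes that the antibodies are used as named. If human-reactive clones are already intended, the Ly6C prediction and the missing TSPO and CD68 remain to be resolved.

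**What to change.** Before the first biopsy, amend section D in three places.

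1. In the panel list, replace each mouse-designated entry with a human-reactive counterpart (for example HLA-DR for I-A/I-E), and state species reactivity and clone for every antibody. For CD161 and CD45R, confirm a human-reactive reagent or substitute one.
2. Remove the IL2RA/CD25 duplicate and add TSPO and CD68. The duplicate frees a channel only if both names were to be stained separately. If the limit is 32 channels and the duplicate holds none of its own, TSPO and CD68 can take channels released by mouse entries. For example, TSPO could take that of Ly6C, since the monocyte marker CD14 is already listed, and CD68 could take that of F4/80.
3. In the Anticipated results paragraph, restate the prediction in markers that the revised panel measures, each with its expected direction. Use the same markers for the correlation in the Endpoints paragraph.

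The cost is a short amendment, replacement reagents and modest validation of the revised panel on human gastric tissue, including intracellular staining for TSPO and CD68. No patient, visit or procedure is added.

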- 2) Ability to provide informed consent
- 3) Type I or II diabetes mellitus
- 4) Gastroparesis defined by gastric retention of Tc-99m >60 % at 2 hrs and/or >10% at 4 hrs on scintigraphy (for DG patients only)
- 5) Average Gastroparesis Cardinal Symptom Index (GCSI) ≥ 3 indicating moderate-severe symptoms (for DG patients only)

Exclusion criteria:

- 1) Women who are pregnant or cannot stop breast feeding for 24 hrs
- 2) Using anti-coagulants, anti-inflammatory medications (NSAIDs, corticosteroids, etc.) or immunosuppressive therapies within the 4 weeks prior (for DG patients only)
- 3) Opioid use within the last 4 weeks of gastric emptying scintigraphy
- 4) 4. Prior gastric surgery
- 5) 5. History of IBD, celiac disease, eosinophilic gastroenteritis, microscopic colitis

Dietary, fluid and other restrictions:

During recruitment, informed consent review, and visits, the subjects were informed and reminded of the following restrictions:

1. No alcohol for 72 hours before 1st visit and until after end of study period
2. Use of tobacco products (last 3 months)

Sites where research will be performed

Mayo Clinic in Rochester, Minnesota

b. Sources of research materials

Research material will be the ¹¹C ER 176 PET/CT images, upper endoscopy with gastric muscle biopsies and cells derived from the biopsies. Additionally, questionnaire responses and medical records will be research materials. Results will be maintained in the research laboratories that are ultimately the sole responsibility of the PI, and will be accessed by a secure password available only to authorized study personnel. Data will be merged for studies of associations by the biostatistician. All of the information collected in this study will be for research purposes only.

c. Potential risks

The potential risks associated with the study are those associated with completing questionnaires, ¹¹C ER 176 PET/CT scan and EUS with biopsies. EUS-guided core biopsy is a safe procedure associated with a low risk of adverse events. Mild self-limiting serosal bruising and/or localized hematoma formation at the sites of EUS biopsies were reported in a small cohort of patients with gastroparesis who underwent EUS-guided FNA biopsy of the gastric muscle. Questionnaires come with a risk of privacy erosion and emotional distress. However, the

questionnaires proposed in the study are extensively validated and well received. Participants will have the option of leaving any question unanswered that makes them uncomfortable.

2. Adequacy of Protection against Risks

a. Recruitment and informed consent

All participants will provide written informed consent using IRB-approved consent forms. The consent form becomes a permanent part of the medical record at Mayo Clinic. All subjects will be given a verbal explanation of the study, provided time to read and understand the written consent form, given opportunities to ask questions and provided a copy of the consent form. Participants will be informed of their right to withdraw from the study at any time without prejudice to their clinical management at Mayo Clinic then or in the future.

Consent will be sought by the PI or the assigned study coordinator, and consent will be documented by the participant's signature on the consent form. Specific information is provided in the Mayo consent form regarding storage and future use of the samples. The participants will be informed that any genetic information collected is not yet pertinent to clinical practice, the information will not be included in the medical record, but will be maintained in a coded fashion accessible only to study personnel. The consent form includes specific details about sharing sequencing data on public databases in a coded fashion at the time of publication. All recruitment material will be approved by the IRB at Mayo Clinic.

b. Protection against risk

Responsible conduct of human research by study personnel

The personnel involved in the study have completed the required education on the protection of human research participants. This is done through IRB's website "Protecting Human Research Participants" online training program. At the conclusion of the instruction, individuals are required to complete a quiz for competency assessment. In addition, [name] has completed CCaTS Core 6001 (Refresher in Responsible Conduct of Research) and Collaborative Institutional Training Initiative (CITI) training on Good Clinical Practice Course for Clinical Trials Involving Drugs. He is also up-to-date on the CITI instruction in human subjects protection. The course is designed to help users understand human subjects protection issues through a web-based program.

Specific risks and precautions

- 1) Survey questionnaires: Questionnaires pose no more than minimal risk to the participants. There is a potential for perception of privacy intrusion. However, the subjects have the right to refuse to answer any of the questions or stop at any time, and there is no penalty for refusing to participate. No complications have been recorded. The proposed questionnaires are validated, widely used, and were received well by the participants.
- 2) ¹¹C ER 176 PET/CT scan: PET scans and the tracers used are generally safe. In a recent study, no adverse or clinically detectable pharmacologic effects were observed with ¹¹C-ER176 for any of the 17 subjects
- 3) EUS-guided core biopsy: Mild self-limiting serosal bruising and/or localized hematoma formation at the sites of EUS biopsies. Other standard risks of an upper endoscopy include pain (abdominal and throat), aspiration and extremely rarely, death. Serious risk of bleeding and frank perforation is rare (<1 in 1000).

3. Potential Benefits of the Proposed Research to the Subjects and Others

The proposed research has the potential to remarkably enhance our understanding of visualizing immune dysregulation in the gastric muscle of patients with diabetic gastroparesis. This will have a downstream effect of identifying immune dysfunction in other GI conditions. Broadly, this can revolutionize assessment of inflammatory milieu in areas that are not easily or safely amenable for a biopsy. As of now, there likely will not be a direct benefit to the gastroparesis patients as we still do not have clear therapies to target immune dysfunction in gastroparesis. Given the anticipated mechanistic insights to the participants in this research proposal, and to others with diabetic gut dysfunction, the benefits outweigh the risks.

4. Importance of the Knowledge to be Gained

The proposed research has the potential to develop a new approach to diagnose immune dysregulation in diabetic gastroparesis, a disorder with unmet clinical need. Specifically, this project is aiming to determine if a special radio ligand ¹¹C ER 176 based PET/CT imaging can detect activated macrophages in the gastric muscle of patients with diabetic gastroparesis. Additionally, these results will be validated using actual assessment of gastric muscle tissue to determine cellular markers that associate with pro- or anti-inflammatory macrophages. This study will open a novel paradigm for assessment of immune dysregulation in the GI tract which will have utility for a broad range of GI conditions. This pilot and feasibility proposal will generate novel preliminary evidence for future investigations in this area and treatment trials. The risks to the participants are fairly low with questionnaires, PET/CT scan and EUS with biopsies which are safe procedures. Given the repertoire of the PI and study team in conducting mechanistic, endoscopic and imaging studies of this nature as well as the precautions taken to minimize discomfort or adverse effects, the overall risk of this study is fairly low. There is a high likelihood (e.g., investigator team's record and expertise, validated methods) of obtaining meaningful, useful information for the proposed aim.

5. Data and Safety Plan

Subject Safety: Adverse Events

Adverse Event Grading

Attribution scale: An adverse event is defined as either an expected side effect that is of a serious nature, or an unexpected side effect regardless of severity. All events will be graded as to their attribution (unrelated to protocol: possibly, probably, or definitely related to protocol). Any event that is reported to either the PI or his designated research associates by the subject or medical staff caring for the subject and which meets the criteria will be documented as such.

Expected risks: These risks will be addressed in the protocol and consent form. The expected risks include:

- Loss of confidentiality through unauthorized release of private medical information. This is unlikely since all data are collected in electronic form and access is protected by user identification ID.
- Questionnaires pose some risk of causing emotional distress but these are validated and widely used questionnaires which are typically well received.
- ¹¹C ER 176 based PET/CT imaging is generally safe and no adverse effects were noted in published studies. However, there is radiation exposure which can be harmful. Additionally, there could be intolerance to the IV injection of radio ligand.
- EUS with core gastric biopsies are generally low risk, especially with an advanced endoscopist like [name] who will perform this procedure on all proposed participants. Adverse effects include abdominal pain, bleeding, and perforation. Rarely, these adverse events can lead to sepsis and death. However, the probability of a serious adverse event is 1 in 2000 or less, making the procedure quite safe.

Plan for Reporting both Anticipated and Unanticipated Adverse Events.

Any adverse event that is reported generates a report, which will be submitted to the Mayo Clinic IRB. The report will include a description of the event, when and how it was reported, as well as any official chart records or documentation to corroborate the event or the reporting of the event. All adverse events will be graded as mild, moderate, or severe. Any severe and/or unanticipated adverse event will be reported within 24 hours to the IRB. All other adverse events will be reported in a timely fashion to the IRB, preferably within 2 weeks. All adverse events will be summarized annually and submitted to the IRB.

Subject Safety: Safety review plan and monitoring

Safety Reviews: The PI will review the safety and progress of this study on a quarterly basis.

Annual Review: The PI will review this protocol on a continuing basis for participant safety and include results of the review in the annual progress reports submitted to the IRB. The annual report will address: (1) whether adverse event rates are consistent with pre-study assumptions; (2) reason for dropouts from the study; (3) whether all participants met entry criteria; (4) whether continuation of the study is justified on the basis that additional data are needed to accomplish the stated aims of the study; and (5) conditions whereby the study might be terminated prematurely.

Data Integrity

Adherence Statement: The DSMP outlined will adhere to the protocol approved by the Mayo Clinic IRB (IRB-C which handles research conducted in the Mayo Clinic CCaTS).

Subject Privacy: Data are kept in strict confidence. The template consent form required by Mayo Clinic's IRB includes appropriate language addressing the risks and confidentiality protection. Confidentiality is assured by the use of study number identifiers assigned to each participant. All data will be identified with the use of the study number identifier to the participant. Participants are assured protection of confidentiality as specified by the HIPAA language contained within the standardized template.

Data Confidentiality.

Database protection: The Mayo Clinic software programs are secured with password protection. All information kept within Excel spreadsheets use a study number identifier. Any electronic communication with collaborators outside the Mayo Clinic would include data identified by study number only. The only people with access to the spreadsheet are the study coordinator and the study statistician. The remaining investigators only review group data that have been summarized by the biostatistician.

Secure storage of biospecimens: Tissue samples collected are submitted to a designated laboratory technologist after anonymizing with a study number that is unrelated to the patient's Mayo Clinic registration number. Thus, the technologist does not have access to clinical information. The database that includes sample numbers and Mayo Clinic numbers is maintained in an Excel spreadsheet by the study coordinator.

G. Sharing Plan

We will share materials and manage intellectual property as described in the NIH Sharing Policies and Related Guidance on NIH-Funded Research Resources including the NIH Public Access Plan for Increasing Access to Scientific Publications and Digital Scientific Data from NIH Funded Scientific Research (February, 2015) and the NIH Genomic Data Sharing Policy (August, 2014).

Following publication, we will share our results, methodology, and reagents with the research community at large in a manner consistent with data/resource sharing policies of the National Institute of Health, the Mayo Clinic and the publishers of the journals where our reports will appear. Should any intellectual property arise which requires a patent, we will ensure that the technology (materials and data) remain widely available to the research community according to the NIH Principles and Guidelines document.

As a means of sharing knowledge, publication of NIH-supported original research in primary scientific journals will be our priority. The PI will concentrate on publishing these findings in a timely manner and acknowledge that the research is supported by the NIH. Upon acceptance, publications will be submitted to the NIH Manuscript Submission (NIHMS) system for open access via PubMed Central.
